For Option B, we will use transcranial alternating current stimulation (tACS), which is one specific form of transcranial electrical stimulation (tES) combined with electroencephalography (EEG) to measure neuroplasticity that is similar to TMS neuroplasticity measurements. In both paradigms, the brain's response to a mild electrical stimulus is recorded. With TMS, a mild electrical stimulus is delivered with electromagnetic induction, and the response is measured with electromyography surface electrodes. With tACS, a mild electrical current is delivered with small electrodes placed on the scalp, and measured with electromyography surface electrodes. These two methods are under the same neurophysiological principles, and thus, yield comparable data.

The practical application of tACS is simple: a low intensity (1-2 mA) alternating electrical current is applied to the scalp to influence underlying cortical excitability, which is measured with non-invasive surface EEG electrodes. Direct current stimulation is presently FDA-approved for extracranial use, and FDA applications for cranial stimulation for management of mood disorder and chronic pain are in progress. The stimulator used in this study is the STARSTIM®-Home system (Neuroelectrics, Inc), a tES home-base system that recently received FDA approval for the Investigational Device Exemption supplemental protocol in a study for tES to be used to treat patients with Major Depression Disorder (MDD) due to COVID-19 related restrictions. STARSTIM®-Home system is capable of recording EEG before, during and after tACS stimulation.

Genetic factors may modify cognitive response to exercise. A common single nucleotide polymorphism of the BDNF gene (Val66Met) impairs activity-dependent release of BDNF.¹⁹ We and others have demonstrated that the Val66Met allele attenuates improvements in cognitive performance after exercise, both in young^{18,20} and old adults²¹. Furthermore, carriers of the apolipoprotein E (APOE) e4 alleles exhibit greater cognitive benefits after exercise through unknown mechanisms,^{22,23} although

IRB Study Number: 20180926

they have greater risk for AD.^{24,25} The effects of genetic factors on response to exercise will only be evaluating in the Option A.

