 - d. Any medical devices (i.e. Cardiac pacemaker, deep brain stimulator, medication infusion pump, cochlear implant, vagal nerve stimulator)
 - e. Intracranial lesion
 - f. Substance abuse or dependence within the past six months
 - g. Exclusively for Option A: TMS Neuroplasticity assessment, as per the TMS Safety Guidelines.¹³
 - i. History of fainting spells of unknown or undetermined etiology that might constitute seizures
 - ii. History of seizures, diagnosis of epilepsy, history of abnormal (epileptiform) EEG or family history of treatment resistant epilepsy

IRB Study Number: 20180926

- Pregnant women
- Vulnerable populations such as prisoners
- People unable to consent themselves
- Subjects who, in the Investigator's opinion might not be suitable for the study

[figure not shown]
6) Number of Subjects

This is not a multi-center study. We will recruit a total of 80 adults. We will use a multifaceted approach by recruiting participants from the Evelyn F. McKnight Brain Institute community memory clinic, and by advertising the study using flyers throughout the University of Miami Miller School of Medicine (UMMSM) and Coral Gables Campuses, the Miami community and participant registries. We will also recruit via online research database tool including the ResearchMatch.org. In addition, we will access University Research Informatics Data Environment (URIDE), and potential subjects will be identified and contacted via the Consent to Contact Initiative.

With a significance level of 0.05, our sample of 80 individuals will provide 80% power to detect a Cohen effect size of 0.36 using a two-sided paired t-test for Aim 1, the effect size associated with improvements in executive function in a recent meta-analysis of healthy adults 55+,²⁶ and an attrition of 20%, not uncommon in exercise intervention trials. In addition, a sample of 80 participants will provide 80% power to detect a correlation of 0.34 between the change in neuroplasticity and the change in cognitive performance.

7) Study Timelines

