- A virtual consenting process will be completed using zoom for healthcare and REDCap e-consent as approved through the Clinical and Translational Science Institute (CTSI). The individual will be sent a REDCap link either through a secure email or through the chat feature of zoom. Once the individual opens the link, they will be asked to share their screen. At that time a trained study personnel will review the informed consent with the individual and answer any question the individual may have about the study. If the individual agrees to participate in the study, they will be asked to sign the e-consent form and provide the study personnel remote access of their web browser to also sign the consent form. The individual will then certify the information and submit the consent. At that time, they will have the option to download or print the completed consent form. A copy can be mailed at the individual's request. Participants will then be mailed a study kit.

Session #1b: Familiarization session- Review items delivered to place of residence using secured zoom (estimated time: 1.5 hours, completed in week one, follow up session may be scheduled as needed)

- Familiarize participant with all of the tools in the study kit.

IRB Study Number: 20180926

- The participant will learn to take their own blood pressure, oxygen saturation, put on the heart rate monitor, and proper safety and cleaning procedures.
- Participants will learn various zoom functions such as sharing screens which will be later utilized in the study.
- Participant will learn how to put on the EEG cap and how to operate the tablet.

Session #2 and #28 Pretest and Post assessment Part 1 (estimated time: 2 hours, completed in week 1)

- TMS plasticity assessment will be replaced with the tACS/EEG plasticity assessment.
- TMS-EEG will not be offered for Option B of the study.

Session #29 Posttest assessment- Part 2 (estimated time: 2 hours, completed in week 1).

- Return Study Kit.

8) Study Endpoints

Neuroplasticity Measures

- **TMS Plasticity Measures**
 - An index of the duration of the TBS-induced modulation of corticospinal excitability (the time-point at which the normalized mean MEP amplitude returns to baseline values) will be defined for each participant.
- **TMS-EEG**

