 - The TMS-EEG integration provides real-time information on cortical reactivity and connectivity. EEG provides exquisite temporal resolution, a direct measure of neuronal activity, and is capable of differentiating inhibitory and facilitatory effects in response to TMS. Contrasting the results of TMS on EEG before and after TBS provides information about cortical plasticity (at the site of stimulation) and resulting network dynamic adaptations.
 - Brain functional connectivity and inter-regional coordination can be directly estimated from EEG's. Spontaneously occurring potentials across EEG channels will be detected prior and following stimulation using already developed event detection algorithms. Measurements following single-pulse TMS provide insights on cortical excitability. The EEG cap will be placed at the beginning of the session and will remain on for the duration of the visit.
- **tACS/EEG Plasticity**
 - An index of change in the tACS-induced modulation of cortical excitability will be defined for each participant. Brain functional connectivity and inter-regional coordination can be directly estimated from EEG's. Spontaneously occurring potentials across EEG channels will be detected prior to and following stimulation using already developed event detection algorithms.

Cognitive performance

- Cognitive performance will be assessed using a neuropsychological test battery. Executive function will be assessed using the Digit Span subtest of the Wechsler Adult Intelligence Scale – Fourth³⁰, processing speed will be assessed using the Trail-Making Test Part B³¹ and the Stroop color-word test²⁹, global cognition will be assessed with the repeatable neuropsychological battery (RBANS)³⁰; and the Delis-Kaplan Executive Function System (DKEFS)³¹ will test for language.

IRB Study Number: 20180926

- Option B: the same cognitive battery, except for the Stroop color-word test, and with the addition of a TestMyBrain.org³² battery of Digit Symbol Matching, Simple and Choice Reaction Time, and Gradual Onset Continuous Performance Test will be used via a secured Zoom Platform.

Gait and postural control

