- The Timed Up-and-Go (TUG) test will be completed. Four, 90-second trials of walking will then be completed to assess gait under normal and cognitive dual task conditions. Standing postural control will be assessed by measuring postural sway with mobile sensors during 2 repetitions each of 30-second trials of standing—two with eyes open, two with eyes closed, and two while performing the serial subtraction cognitive task.
- Option B: The Timed Up-and-Go (TUG) test will be completed and supervised via a secured Zoom Platform.

Genetic Testing

- Blood samples will be collected for BDNF levels and DNA to assess brain-derived neurotrophic factor (BDNF) Val66Met polymorphism and the presence of apolipoprotein-E (APOE) e4 allele. We will store blood samples for future examination of other potential genetic, epigenetic, metabolic or pro-inflammatory markers.

Aerobic Capacity

- The Incremental Shuttle Walking Test (ISWT) will be performed to determine maximal walking velocity and walk distance. These values will be used to predict VO² peak changes over time as a measure of aerobic capacity. The test will be used to dose the aerobic exercise intensity. Additionally, changes in VO² peak will be assessed for relationship with neuroplasticity and cognitive changes. The participants will be closely monitored (Heart rate, Blood pressure, rate of perceived effort) prior, during and after the test.
- Option B: We will adapt our exercise assessment to a submaximal aerobic capacity assessment using the 1-minute Sit-to-Stand Test (1-MSTST)³³ which can be completed in the participant's home. The 1-MSTST will be performed to determine maximal repetitions completed in one minute without using upper limbs. These values will be used to predict changes in aerobic capacity over time. The test is submaximal and will be used to dose the aerobic exercise intensity. Additionally, changes in aerobic capacity will be assessed for any relationship with neuroplasticity and cognitive changes. The participants will be closely monitored (heart rate, blood pressure, rate of perceived effort, and oxygen saturation) prior to, during and after the test.

9) Procedures Involved*

Study Design

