In the univariate analysis, we will compare the cognitive performance (overall and by domain) before and after exercise, using paired t-test to test for **Specific Aim 1**. For **Specific Aim 2**, we will examine the relationship between the change in TMS neuroplasticity and the change in cognitive performance using Pearson product-moment correlation coefficient. For **Specific Aim 3**, we will compare mean change in cognitive performance across subgroups by genotype using F- test. In the multivariable analyses, we will adjust for baseline characteristics (age, sex, race- ethnicity, education) using mixed effect modeling to quantify improvements in cognitive performance after exercise (**Specific Aim 1**), and to determine an association between changes in TMS plasticity, cognitive performance and changes in aerobic capacity (**Specific Aim 2**). We will use modification models by including interaction terms (time-by-genotype) to explore the relationship between change in cognitive performance after exercise and BDNF levels, Val66Met, and APOE e4 status (**Specific Aim 3-Option A only**).

12) Provisions to Monitor the Data to Ensure the Safety of Subjects*

Monitoring the safety of participants with respect to TMS neuroplasticity assessment

TMS has been used in a growing number of laboratories worldwide since 1984. A series of adverse events have been identified since then, and have been thoroughly reviewed for the development of recommended safety guidelines and precautions for the use of TMS, first at a consensus conference at the NIH in June, 1996 and, more recently, in 2008 in Siena (Italy), in a

IRB Study Number: 20180926

meeting of an international panel of TMS experts ([The Safety of TMS Consensus Group](#)).

The principal investigator will ensure that these guidelines are well-known by all study investigators and will carefully follow these updated safety guidelines in the present study. Additionally, we will track and report any adverse events that may occur.

Monitoring the safety of participants with respect to tACS neuroplasticity assessment

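### Aim 2 is defined on TMS plasticity and powered on all 80 participants, but Option B participants have no TMS; Aim 1 also states one weekly dose where the two options prescribe 150 and 120 work minutes.

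*Combined protocol and SAP*

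**What the plan says.** **Aim 2.** Section 11 (Data Analysis) says "we will examine the relationship between the change in TMS neuroplasticity and the change in cognitive performance" by Pearson correlation. Its power statement names TMS and counts 80 participants. Section 6 makes the same claim without naming TMS: "80% power to detect a correlation of 0.34 between the change in neuroplasticity and the change in cognitive performance". For Option B, Section 7 says "TMS plasticity assessment will be replaced with the tACS/EEG plasticity assessment".

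Section 8 defines the two plasticity measures differently. Option A uses "An index of the duration of the TBS-induced modulation of corticospinal excitability", the time until the evoked response returns to baseline. Option B uses "An index of change in the tACS-induced modulation of cortical excitability", taken from EEG. Aerobic capacity is VO2 peak predicted from a shuttle walk in Option A and repetitions in a one-minute sit-to-stand test in Option B.

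Two other sentences bear on whether Option B belongs in Aim 2. Section 4 says of TMS and tACS: "These two methods are under the same neurophysiological principles, and thus, yield comparable data". Section 8 says of Option B that "changes in aerobic capacity will be assessed for any relationship with neuroplasticity and cognitive changes".

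**Aim 1.** Section 2 names 150 minutes per week. The analysis is a paired t-test before and after exercise, plus a model in which "we will adjust for baseline characteristics (age, sex, race- ethnicity, education) using mixed effect modeling". Only Aim 3 is restricted to Option A. Section 9 describes walking or trotting in Option A, and home equipment or a body-weight circuit in Option B. It gives Option B five blocks of eight minutes' work and two minutes' rest, three times a week.

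**The concern.** The Aim 2 analysis variable does not exist for anyone enrolled in Option B, yet the power claim counts every participant. Two readings are possible, and neither is fully specified.

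- **Option A only.** The sample is smaller than the one the power statement uses, and the shortfall grows with each Option B enrolment.
- **Pooled.** A duration and an EEG change index would enter one correlation, and two different capacity measures one model, with no option term and no common scale. A difference between options in mean change on both variables would then shift the pooled correlation even if there were no association within either option.

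For Aim 1 the stake is smaller. A reader is told that the programme is 150 minutes per week and sees one overall change. Nothing planned shows whether that change is similar in people prescribed 150 minutes and people prescribed 120.

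**Working it through.** **Inputs from the documents.** Two-sided alpha 0.05, 80 enrolled, 20% attrition, d = 0.36 (Aim 1), r = 0.34 (Aim 2), all from Sections 6 and 11. Completers: 80 × 0.8 = 64.

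**Assumption.** The split between options is not given, and Option B may be chosen by preference. I use 48, 42 and 32 Option A completers out of 64 as the main range, and add 16 because Section 3 made Option B the only route for a time.

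**The plan's own figures.**
- Aim 1, paired t-test, noncentral t, n = 64, d = 0.36: power 80.9%. The stated 80% reproduces.
- Aim 2, power = Φ(atanh(r)·√(n − 3) − 1.96), with atanh(0.34) = 0.354. At n = 64: 0.354 × √61 = 2.766, and Φ(0.806) = 79.0%. The stated 80% reproduces, on 64 completers who all contribute a plasticity change.

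**Aim 2 if Option A only.** Same power formula; detectable r at 80% power = tanh((1.960 + 0.842)/√(n − 3)).

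| Option A completers | Power for r = 0.34 | Detectable r |
|---|---|---|
| 64 | 79% | 0.34 |
| 48 | 66% | 0.39 |
| 42 | 60% | 0.42 |
| 32 | 48% | 0.48 |
| 16 | 25% | 0.65 |

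**Aim 2 if pooled.** Let p be the Option B share, and let Dx and Dy be the option gaps in mean plasticity change and mean cognitive change, in within-option SDs. With no association inside either option, the pooled correlation is

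p(1 − p)·Dx·Dy / √[(1 + p(1 − p)Dx²)(1 + p(1 − p)Dy²)].

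Example with p = 0.5, Dx = 1, Dy = 0.36: 0.25 × 0.36 = 0.09; √(1.25 × 1.0324) = 1.136; r = 0.08. Rejection rates of the pooled Pearson test at nominal 5%, from simulation (n = 64, 40,000 runs, Option B shares of about 25%, 35% and 50%):

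| Assumed gaps (plasticity, cognition) | False-positive rate |
|---|---|
| 1 SD, 0.072 SD | 5% |
| 0.5 SD, 0.5 SD | 7% |
| 1 SD, 0.36 SD | 8% to 9% |
| 1 SD, 1 SD | 24%, 31%, 36% |

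The 0.072 is 20% of 0.36, a cognitive gap proportional to the dose difference. The 0.36 is the whole planned effect in one option and none in the other. All gaps are assumptions.

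**Aim 1 dose.** Option A: a 60-minute session less 10 minutes of warm-up and cool-down gives 50; 50 × 3 = 150 per week; 50 × 24 = 1200 in total. Option B: 5 × 8 = 40; 40 × 3 = 120 per week; 40 × 24 = 960 in total. 1 − 120/150 = 20% less prescribed work. Option B reaches 150 only if its rest breaks, or its warm-up and cool-down, are counted; counting warm-up and cool-down would put Option A at 180.

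**Aim 1 precision by option.** 95% half-widths in SDs of change. Pooled: t(0.975, 63)/√64 = 0.25. Contrast between options: t(0.975, 62)·√(1/n1 + 1/n2) = 0.58 at 48/16, 0.53 at 42/22 and 0.50 at 32/32. Equipment against body weight within an Option B of 32 (16/16): 0.72. Each contrast half-width exceeds the planned effect of 0.36.

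**The case against.** The strongest reply on Aim 2 is that the analysis section does not describe pooling. It names TMS plasticity throughout. Section 4 is background rationale, and the Section 8 sentence on Option B fits a separate Option B analysis equally well. This stands. It disposes of any claim that the plan pools the two instruments, but not of the power problem, because under that literal reading the 80-participant figure is wrong.

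A reader might infer from the last row of the simulation table that Aim 2 faces a false-positive rate of 24% to 36%. The documents do not support that. It needs a 1-SD gap between options in both changes, and for cognition that is nearly three times the planned effect of 0.36. Modest gaps give about 5% to 9%.

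On Aim 1, each participant is their own control, so an option main effect alone would not move the before-after estimate. Pooling is itself an inference from the sample of 80 and the absence of a restriction; no sentence states it. The 20% is prescribed work, not delivered dose: Option A also allows rest on request, and both sessions last 60 minutes. Nor should a reader infer lower intensity in Option B, since its heart-rate and exertion targets are close to those of Option A. All of this stands, and it limits the Aim 1 point to description.

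**Conclusion.** The concern holds for Aim 2 as written. The variable named in the analysis is not collected in Option B, so the stated 80% power for r = 0.34 is not delivered once participants enrol there: about 66% at 48 Option A completers, 60% at 42 and 48% at 32. These figures rest on 20% attrition and an assumed split. If pooling was intended, the plan lacks an option term and a common scale. The resulting bias is small for modest option gaps and larger only for large ones, and the documents support no particular gap.

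For Aim 1, the single 150-minute dose does not describe Option B, which prescribes 120 minutes of work, and change is not planned to be shown by option. This is a reporting gap. It does not show that the pooled estimate is biased or that the sample size is wrong; the Aim 1 power figure reproduces.

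**What to change.** **Aim 2**
1. State that the TMS analysis is Option A only, and restate power or detectable r for the expected number of Option A completers.
2. Report the Option B tACS/EEG association separately.
3. Make any combined analysis secondary. Standardise plasticity and capacity changes within option, include option in the model, and label it as assuming a common association across two different instruments. Standardising puts them on one scale; it does not make them one construct.

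**Aim 1**
1. State the dose by option: 150 minutes per week in Option A, 120 minutes of work in Option B.
2. Keep the pooled paired t-test and mixed model as the main analysis.
3. In a separate model with an option-by-time interaction, report mean change with 95% CI by option, and by mode within Option B. Present it as an unpowered description that cannot separate exercise mode from setting, test battery, participant preference or calendar period.

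**Cost.** One recorded variable, one secondary model, one table and a revised Aim 2 population and power statement, with no new data collection. The main Aim 1 analysis keeps its 81% power. The price is imprecise estimates by option and a less favourable Aim 2 power figure.

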This is an investigator-initiated open label study in neurologically healthy sedentary adults. Participants will undergo a total of 29 or 31 sessions, including the screening session, three to four pretest (baseline) assessments, 24 aerobic exercise sessions and three to four post-test assessments. For option A, assessments will take place at the Neuromotor Plasticity Lab located at Lois Pope Life Center located at [name] and aerobic exercise visit will take place at either the UMMSM Medical Wellness Center or the UM Coral Gables Wellness Center. For option B, assessments and exercise sessions will take place in the participant home as they are monitored by a trained study member. An illustration of the experimental design is provided below:

Methods:

Subjects will participate in the Option A pending appropriateness based on current University of Miami recommendations and standard operating procedures as it relates to the COVID-19 pandemic. Given the COVID-19 pandemic, it is worth of note that potential participants may remain less enthusiastic about in-person procedures for an undetermined length of time. Thus, even in the event that the study team obtains approval to resume activities as per Option A based on University guidelines, we would like to continue to offer Option B according to participant preference. All testing procedures described for the Option A will be adapted (as feasible) for the Option B. Testing procedures that differ for the Option B are described and noted in the Option B methods.

OPTION A METHODS

TMS Plasticity

Subjects will come in for a total of 2 plasticity visits (pre and post training). We will measure plasticity in the motor cortex of the dominant hand.

Subjects will be set up in a chair with EMG electrodes placed on the first dorsal interosseus (FDI) on the dominant hand to measure motor threshold over in the corresponding (contralateral) motor cortex (M1). The motor threshold serves as the basis for the following TMS-measures over the motor cortex. When administering TMS, the figure of eight coil will be placed tangentially to the scalp with the handle pointing posterior for all stimulations. We will proceed with determining motor threshold and conduct TMS (single pulse TMS and TBS) over the dominant motor cortex. After removing the EMG equipment from the subject, a post TMS safety evaluation will be conducted.

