With a significance level of 0.05, our sample of 80 individuals will provide 80% power to detect a Cohen effect size of 0.36 using a two-sided paired t-test for **Aim 1**, the effect size associated with improvements in executive function in a recent meta-analysis of healthy adults 55+,⁴² and an attrition of 20%, not uncommon in exercise intervention trials. In addition, a sample of 80 participants will provide 80% power to detect a correlation of 0.34 between the change in TMS neuroplasticity and the change in cognitive performance for **Aim 2**, and 80% power to detect an R-Squared of 0.11 attributed to a genetic modification in the change in cognitive performance using an F-Test for **Aim 3 (Option A only)**. We expect an overall improvement in cognitive performance after aerobic exercise. Most robust improvements are expected in executive function as previously shown in elderly, but also in other cognitive domains such as processing speed and attention.¹¹

Baseline characteristics will be summarized as means \pm standard deviation or medians (interquartile ranges) for continuous variables and as frequency (%) for categorical variables. Normality for the distributions of continuous variables will be visually assessed and statistically tested. If the normality assumption is questionable, Box-Cox transformation will be used to reduce the skewness in the indicated analyses or non-parametric tests will be used. All statistical tests will be conducted against a 2-sided alternative hypothesis, employing a significance level of 0.05.

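### Aim 3 names no covariate term that acts on change, so its multivariable genotype result gives essentially no control for ancestry; the possible bias is modest under mild assumptions and inexpensive to reduce.

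*Combined protocol and SAP*

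**What the plan says.** The design has no randomisation and no control arm: "This is an investigator-initiated open label study in neurologically healthy sedentary adults". Section 11 (Data Analysis) gives Aim 3 two analyses.

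- Univariate: "we will compare mean change in cognitive performance across subgroups by genotype using F- test". No covariates are attached.
- Multivariable: "We will use modification models by including interaction terms (time-by-genotype) to explore the relationship between change in cognitive performance". The modifiers named there are BDNF levels, Val66Met and APOE e4 status. Time-by-genotype is the only interaction named.

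Between these stands the covariate sentence: "we will adjust for baseline characteristics (age, sex, race- ethnicity, education) using mixed effect modeling". It goes on to name Specific Aims 1 and 2, not Aim 3.

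No time-by-race-ethnicity term, stratified analysis or ancestry marker is described. Section 9 (Blood Collection) lists rs6265, rs429358, rs7412 and APOE4 as the genotyping. Section 2 (Objectives) words Aim 3 as exploratory and limits it to Option A. The same Data Analysis section gives Aim 3 its own power claim: "80% power to detect an R-Squared of 0.11 attributed to a genetic modification in the change in cognitive performance using an F-Test".

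**The concern.** Aims 1 and 3 ask different kinds of question. In Aim 1 each person is their own control, so a fixed characteristic such as race-ethnicity cannot confound the mean change. Aim 3 compares different people, grouped by a variant whose frequency may vary with ancestry. If race-ethnicity groups also differ in change, through training response or simply through retest gain (which a single-arm study cannot separate), that difference leaks into the genotype contrast. A genetic modifier can then appear where there is none, or a real one can be masked.

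The wording also invites misreading. A result from the multivariable model would normally be taken as adjusted confirmation of the F-test, when the covariates, if present at all, sit where they cannot act on change.

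**Working it through.** **1. The plan's own figure.** Inputs from sections 6 and 11: "We will recruit a total of 80 adults", "an attrition of 20%, not uncommon in exercise intervention trials", R-squared 0.11, and two-sided 0.05. Completers: 80 × 0.8 = 64. Noncentral F with λ = n·R²/(1 − R²) = 64 × 0.11/0.89 = 7.91 and 1 numerator df gives power 79.1%. Taking n = 80 with 2 df gives 79.4%. The stated 80% reproduces. The other two power claims also fit 64 completers (d = 0.36: 81.0%; r = 0.34: 79.0%), so 64 is used below.

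**2. Why a main effect does not help.** For person i at visit t (0 or 1), with genotype G and race-ethnicity R:

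y = a + u_i + βt + γG + δ(t×G) + ρR + error.

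Subtracting the visits gives change = β + δG + error. The ρR term cancels. Only a term τ(t×R) would survive the subtraction.

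Two simulated complete data sets (single draws, the first with n = 64) show the algebra at work. Time-by-genotype estimates (SE):

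| Model | Draw 1 | Draw 2 |
|---|---|---|
| No race-ethnicity term | 0.370 (0.229) | 0.432 (0.236) |
| Race-ethnicity main effect | 0.370 (0.229) | 0.432 (0.236) |
| Time-by-race-ethnicity added | 0.045 (0.235) | 0.300 (0.238) |

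In draw 1 the raw difference in mean change is also 0.370, and regressing change on genotype and race-ethnicity gives 0.045.

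**3. With dropouts.** When 20% of post values are missing, the identity becomes an approximation. In one draw the estimates were 0.242 (no race-ethnicity), 0.251 (main effect) and 0.146 (interaction).

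**4. Size of the bias.** With τ = gap in mean change between two race-ethnicity groups,

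bias = τ × [P(R=1 | carrier) − P(R=1 | non-carrier)].

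The documents give no carrier frequencies, race-ethnicity mix or change by group, so all of these are assumptions: two equal groups, no true genotype effect, gaps in SD of change.

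- Carriers 20% v 45%: 0.45/0.65 − 0.55/1.35 = 0.692 − 0.407 = 0.285
- Carriers 10% v 50%: 0.50/0.60 − 0.50/1.40 = 0.833 − 0.357 = 0.476

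Multiplying by the gap gives the bias. Simulation at n = 64 gives the false-positive rate of the unadjusted test (ranges span separate runs):

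| Gap (SD) | 20% v 45%: bias, false positives | 10% v 50%: bias, false positives |
|---|---|---|
| 0.2 | 0.06, 5.7% | 0.10, 6.1-6.2% |
| 0.3 | 0.09, 6.0-6.6% | 0.14, 8.0-8.4% |
| 0.5 | 0.14, 8.2% | 0.24, 12.8-14.4% |
| 0.8 | 0.23, 12.1-12.2% | 0.38, 24.8-25.4% |

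With closer carrier rates (20% v 35%) the figures are 5.1% at 0.2 SD, 6.2-6.4% at 0.5 SD and 7.6-7.8% at 0.8 SD. With equal carrier rates, or no gap in change, the rate stays at about 5%.

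**5. Scale.** If 30% are carriers, R² = 0.11 corresponds to a difference d with 0.3 × 0.7 × d² = 0.11/0.89, so d = 0.77 SD. Bias in the 10% v 50% column is therefore about one eighth (0.10/0.77) to one half (0.38/0.77) of the effect the plan is powered to find.

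**6. After adjustment.** Entering race-ethnicity on the change scale returned the rate to 4.6-5.6% and the mean bias to about zero. This holds by construction, because the simulated confounder is measured without error.

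**The case against.** **Silence is not exclusion.** The covariate sentence opens the multivariable paragraph, the Aim 3 sentence follows in it, and that sentence speaks of interaction terms in the plural. A reader might infer that the plan rules out race-ethnicity adjustment for Aim 3. It does not say so. What stands is narrower: no covariate term acting on change is named, and the natural carry-over (main effects) would not supply one. A change-score model with the four covariates would be enough, but the time-by-genotype wording points to repeated measures.

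**The two Aim 3 analyses are not simply one test.** That inference is tempting but too strong. BDNF level is not a genotype and is tested only in the modification model, so the F-test does not duplicate it. Allele frequency is not the mechanism there, although the same covariate gap applies. For Val66Met and APOE e4 the identity needs complete pairs, whereas the plan expects 20% attrition and section 13 keeps data from those who withdraw. With 80 enrolled and 16 baseline-only, one simulated draw gave 0.109 without and 0.083 with a race-ethnicity main effect, against 0.065 in completers. These shifts are small and do not remove the confounding.

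**The large rates need large assumptions.** No part of the documents shows that change differs by race-ethnicity. The planned mean change is 0.36 SD, so a 0.8 SD gap between equal groups implies 0.36 ± 0.40, that is 0.76 in one and −0.04 in the other. Sixty-four is also an upper figure for Aim 3, since only Option A is genotyped and section 3 makes Option B the only route until in-person work resumes. At n = 32 a 0.3 SD gap gives 5.7% and 6.6%, and the worst case falls to about 15%. This objection stands and limits the severity.

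**Conclusion.** The concern holds in a limited form. As written, neither Aim 3 genotype analysis adjusts change for ancestry, and carrying over the listed covariates as main effects would leave that essentially unchanged. This follows from the model with complete pairs and is a close approximation with baseline-only dropouts.

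Whether it biases the result depends on two facts the documents do not give: differing carrier frequency and differing cognitive change across race-ethnicity groups. Both are needed. On the assumed values, the false-positive rate against a nominal 5% is about 6-8% at a 0.2-0.3 SD gap, 8-14% at 0.5 SD and 12-25% at 0.8 SD. A reader might take the 25% figure as the expected error rate. The documents do not support that; it belongs to the most extreme scenario and shrinks with a smaller Option A sample. Because Aim 3 is exploratory, severity is minor to moderate.

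**What to change.** In the Aim 3 model, enter time-by-race-ethnicity alongside time-by-genotype or time-by-BDNF level. Add time-by-age, time-by-sex and time-by-education as the Option A sample allows. Equivalently, regress change on the modifier plus these covariates. Report this as the Aim 3 estimate, with the F-test as its unadjusted companion. State that race-ethnicity is a proxy, so the adjustment reduces ancestry confounding but may not remove it.

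The covariates are already named in the plan, so the change is a line or two of text. At 64 completers, 4 to 7 extra degrees of freedom move power from 79.1% to 79.0% or 78.9% if the covariates are unrelated to genotype. Where they are related, the standard error widens somewhat (0.229 to 0.235 in draw 1; 0.260 to 0.277 in another simulated example with all four covariates interacted with time). The cost grows if Option A is small; coarse race-ethnicity categories should then be used.
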